Following informed consent, patients will undergo 2x1 block randomization to ensure equal allocation to each intervention group. Randomization will be performed by study personnel and will be blinded as there will be placebo injections for patients randomized into group two and the same number of injections would be used regardless of intervention arm.

Data Collection:

Verbal NRS, pain assessment data, opioid use, and time to first opioid breakthrough dose will be collected as previously described. Portable spirometry will be used daily to objectively and serially assess lung function. Additional data collection points include patient sex, age, weight, body mass index, body surface area, injury severity score, chest abbreviated injury score, and ICU and hospital length of stay. Safety will be evaluated by the occurrence of *a priori* serious adverse events. Costs will be evaluated utilizing hospital and pharmacy databases.

Schedule of subject identification and data collection

Subjects will be identified based on inclusion criteria at the time of admission to the trauma service following evaluation in the emergency department. Subjects meeting inclusion criteria will be enrolled within 6 hours of admission. Vitals monitoring will occur during the intercostal nerve block procedure and continue by telemetry for the next 96 hours or until hospital discharge, whichever occurs first.

7. Specimen collection:

No serum assays are necessary for this study and will not be collected.

8. Potential Benefits:

Blunt chest wall trauma remains a common injury seen in non-intentional injury-related deaths. It accounts for nearly 10% of trauma-related emergency department visits worldwide and is associated with high morbidity and mortality. This morbidity and mortality are influenced by the pain experienced by these events which can involve rib or sternal fractures as instigating stimuli.

Uncontrolled analgesia following rib fractures can result in intubation, pneumonia, prolonged length of stay, and death. Achieving adequate pain control in native airway patients prevents clinical challenges. Multimodal analgesia regimens are necessary to optimize patient outcomes and prevent untoward effects of opioid analgesia (e.g., hypotension; bradycardia; central nervous system depression; respiratory depression).

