Consequences of poorly controlled pain associated with rib and/or sternal fractures as well as opioid use have been previously outlined above. Risks of liposomal bupivacaine include major and minor adverse events (Tables 1 and 2). Risks will be mitigated by appropriate exclusion of patients with low and high body weights as well as known cardiac history as previously described to minimize pharmacodynamic failure or excess.

Table 9.1. Adverse events occurring in >2% of patients in any treatment group^{15,17,31}

Adverse Event	Bunionectomy ^{17, 20}		Hemorrhoidectomy ^{18, 20}	
	Liposomal Bupivacaine 106 mg (n=97)	Placebo (n=96)	Liposomal Bupivacaine 266 mg (n=95)	Placebo (n=94)
Any treatment-emergent adverse event	58 (59.8)	65 (67.7)	16 (16.8)	17 (18.1)
Gastrointestinal disorders				
Nausea	41 (42.3)	38 (39.6)	8 (8.4)	13 (13.8)
Vomiting	39 (40.2)	36 (37.5)	2 (2.1)	1 (1.1)
Painful defecation	27 (27.8)	17 (17.7)	2 (2.1)	4 (4.3)
Nervous system disorders				
Dizziness	20 (20.6)	30 (31.3)	0 (0.0)	0 (0.0)
Headache	11 (11.3)	25 (26.0)	0 (0.0)	0 (0.0)
Somnolence	5 (5.2)	8 (8.3)	0 (0.0)	0 (0.0)
Skin and subcutaneous tissue disorders				
Skin and subcutaneous tissue disorders	8 (8.2)	7 (7.3)	0 (0.0)	0 (0.0)
Pruritus, generalized	5 (5.2)	6 (6.3)	0 (0.0)	0 (0.0)
Abnormal laboratory investigations	5 (5.2)	3 (3.1)	4 (4.2)	3 (3.2)

Data are no. (%) of patients.

Table 9.2. Incidence of serious adverse events occurring in >1 patient in any treatment group³⁰

	n (%)		
	Liposome Bupivacaine		
	≤266 mg (n = 545)	Bupivacaine HCl (n = 446)	Placebo (n = 190)
Any serious AE	6 (1.1)	24 (5.4)	2 (1.1)
Arthrofibrosis	0	3 (0.7)	0
Cellulitis	0	0	0
Congestive cardiac failure	0	0	0
Atrial fibrillation	0	2 (0.4)	0
Sedation	0	0	0
Hypoglycemia	0	2 (0.4)	0
Deep vein thrombosis	0	2 (0.4)	1 (0.5)

Cardiac and neurotoxicity that are generally seen with increased serum bupivacaine concentrations (i.e. >2000 ng/mL) should serve minimal risk as concentrations seen in previous studies using the maximum FDA-approved dose of 266 mg of liposomal bupivacaine measured maximum concentrations of 867 and <300 ng/mL each.^{15, 28-29} Patients will require and be monitored by a central cardiac monitoring unit to assess for any changes in heart rate or rhythm for the first 96 hours at minimum.

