Myalgia	No interference with activity	Some interference with activity	Significant; prevents daily activity	ER visit or hospitalization

Table 9.4 extracted from: Guidance for Industry, Toxicity Grading Scale for Healthy Adult and Adolescent Volunteers Enrolled in Preventive Vaccine Trials, U.S. Department of Health and Human Services, Food and Drug Administration, Center for Biologics Evaluation and Research, August 2016

Treatment of cardiovascular and neurologic adverse events

- Local anesthetic systemic toxicity
 - Treatment will be initiated as recommended as the American Society of Regional Anesthesia and Pain Medicine, according to the society's checklist (Appendix)
- Treatment will include: transfer to intensive care unit setting if not already in intensive care unit, continuous hemodynamic monitoring for at least 24 hours, appropriate airway management with assistance from respiratory therapy and a critical care consultant as needed, cardiovascular stabilization and assistance from a critical care consultant as needed, administration of Lipid Emulsion therapy, as per ASRA checklist in Appendix, Neurology consult for any observed systemic neurologic toxicity (including change in vision, mental status change, persistent headache, seizure), Cardiology consult for any arrhythmias that persist greater than 30 minutes, beyond initial appropriate medical treatment, or result in hypotension with systolic blood pressure < 80mmHg.

10. Data Safety monitoring plan and/or DSMB:

Patients will be screened for the adverse events described above.

Adverse events will be continuously assessed on an ongoing basis by [name], medical monitor. Study will be stopped if:

- **Adverse events probably/likely or certainly related to study drug, regardless of severity, occur in > 10% of enrolled patients, or**
- **Serious/life-threatening adverse events, regardless of causality, occur in > 2% of enrolled patients.**

11. Data Analysis:

Primary Endpoint

- 1) Compare opioid requirements (in morphine equivalents) between trauma patients with rib and/or sternal fractures receiving liposomal bupivacaine versus standard of care.

Secondary Endpoints

- 1) Compare clinical outcomes and treatment failures including:
 - a. Development of pneumonia, defined as >100,000 cfu/mL bacteria on bronchoalvelolar lavage, or clinically with leukocytosis, pulmonary infiltrate and fever
 - b. Median patient analgesic score by verbal NRS

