 - c. Median time to first breakthrough opioid rescue dose
 - d. Incentive spirometry serial volume capacity
 - e. ICU LOS
 - f. Hospital LOS
 - g. Use of additional analgesia adjuncts
 - i. Epidural catheter
 - ii. Non-opioid analgesics (e.g., non-steroidal anti-inflammatory drugs; gabapentin; pregabalin; carbamazepine; ketamine; acetaminophen)
- 2) Perform a cost-effectiveness analysis
- 3) Calculate dose and exposure of lidocaine or bupivacaine over time from Lidoderm patches, intercostal nerve blocks, or epidural catheters

Statistical analyses will be performed using SAS. An intention-to-treat model will be used for data analysis. Patients randomized into the treatment arm will be included in the primary outcome analysis. Patients withdrawn from the study will have data included up to the point of withdrawal. Nominal data will be reported using frequencies of occurrence and proportions as appropriate. Continuous data will be reported using means and standard deviations or medians and

interquartile ranges as appropriate per distribution. Hypothesis testing for nominal data will be performed using the Fisher's exact test or chi square test as required based on sample size. Continuous data will be compared using student's t-test/ANOVA or rank sum/Kruskal-Wallis ANOVA for normally distributed and non-normally distributed data, respectively as appropriate. A p-value < 0.05 will designate statistical significance. Costs associated with the cost-effectiveness analysis will be pulled from hospital and pharmacy databases.

Given the pilot nature of the study, a total of 200 patients will be enrolled. Assuming a 96-hour requirement of 250-mg oral morphine equivalents (approximately 12.5-mg IV hydromorphone), we anticipate a 20% reduction to 200-mg oral morphine equivalents (approximately 10-mg IV hydromorphone) resulting in an expected difference in means of 50 mg and an anticipated standard deviation of 50 mg. To achieve an 80% power with an alpha of 0.05 for this primary outcome, the goal enrollment is 200 patients.

12. Data storage and confidentiality (include sample storage if applicable)

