This project will use Medidata Rave® as its Electronic Data Capture (EDC) software, which is a robust EDC platform for capturing, managing and reporting clinical research data. This system includes a robust query management system based on the Data Quality Plan, which will identify data quality checks to be programmed into the database design. Frequent monitoring of the database throughout the study will allow for corrective action to be taken quickly if problems are identified with the data collection process. The database will be password protected and appropriately secured such that only authorized study personnel will have access to the data. Data will be maintained in a confidential manner with regular reminders of the need for confidentiality provided from the senior investigator. A single subject log will be kept by the principal investigators for matching patient study number, initials, medical record number, and admission date (attached). Once assigned to the log, patients will only be evaluated using their de-identified, study number. Data entered into the electronic database will be de-identified.

Once the study has been completed, the subject log will be destroyed and only the de-identified electronic database will be kept. Only study personnel will have access to the data.

13. Study Population

UCMC is an urban, academic American College of Surgeons-verified Level 1 trauma center that treats over 3500 trauma patients each year. Patients admitted to the UCMC trauma service are eligible for enrollment. Patients will be screened on admission or identified per the daily trauma census. Trauma team

physicians may also contact study personnel daily once a patient is identified as a potential candidate. Study personnel will screen subjects for inclusion and exclusion. If patient meets inclusion criteria, then consent will be administered by study personnel (see section 14).

Inclusion Criteria

- a. Patients with an anticipated length of stay of at least 72 hours
- b. Trauma patients with two or more rib or sternal fractures
- c. Patients demonstrating the inability to achieve greater than 50% predicted inspiratory capacity based on ideal body weight using IS within the first 24 hours of admission (Appendix)
- d. Adults age 18 and older

Exclusion Criteria

- a. Patients with a known allergy to bupivacaine
- b. Respiratory failure requiring intubation within 24 hours prior to enrollment

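### The primary opioid endpoint states no window or time zero, and a 96-hour total built from data that stop at discharge or withdrawal counts unobserved hours as zero use

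*Combined protocol and SAP*

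**What the plan says.** Section 11 states the primary endpoint as: "Compare opioid requirements (in morphine equivalents) between trauma patients with rib and/or sternal fractures receiving liposomal bupivacaine versus standard of care". The unit is given. The start of counting, the length of the window and the summary measure (total or rate) are not. The aims in sections 3 and 4 add nothing on these points, and section 6 converts opioid doses to oral morphine equivalents without attaching a period.

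The 96-hour figure enters later in section 11, in the sizing paragraph: "Assuming a 96-hour requirement of 250-mg oral morphine equivalents", followed by "we anticipate a 20% reduction to 200-mg oral morphine equivalents". That paragraph treats the quantity as the primary outcome: "To achieve an 80% power with an alpha of 0.05 for this primary outcome, the goal enrollment is 200 patients". The wording implies a cumulative total.

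Four other provisions bear on whether 96 hours can be observed:
- Section 13, inclusion criterion a: "Patients with an anticipated length of stay of at least 72 hours". The stay is only anticipated, and the start of its clock is not given.
- Section 5 (Study design) and the end of section 13 follow patients for outcomes until discharge. After discharge, section 6 provides contact only for patients with serious adverse events.
- Section 6 foresees discharge before 96 hours: monitoring is to "continue by telemetry for the next 96 hours or until hospital discharge, whichever occurs first".
- Section 11 keeps a withdrawn patient's data up to the time of withdrawal. It has no rule for discharge or death before 96 hours, and take-home opioids are not mentioned.

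**The concern.** In a cumulative total, fewer observed hours means fewer milligrams. A patient who leaves at 72 hours, or who is withdrawn during the injections after a severe reaction (section 6), looks like a low opioid user whatever was taken afterwards.

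Time of discharge is not neutral here. Section 3 lists a shorter stay among the study's purposes, section 8 names less hospital time as a hoped-for benefit, and section 11 makes hospital length of stay a secondary endpoint. If the drug does shorten stay, more of its patients will have truncated totals, and an effect on stay will be read as an effect on opioid use. Opioid use that was never recorded cannot be recovered at analysis, so the point has to be settled in the protocol.

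**Working it through.** **Inputs from section 11.** 96-hour means of 250 mg (control) and 200 mg (treated), difference 50 mg, SD 50 mg. Arm size of 100 is from section 5. **Assumed, because the documents give no figure:** the share *p* of each arm discharged at 72 hours, and the fraction *f* of 96-hour use that falls after discharge.

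**The plan's own figures.** 20% of 250 mg is 50 mg, so the difference is reproduced. The sample size is not: 2 × (1.96 + 0.84)² × 50²/50² = 15.7, so 16 per arm and 32 in total, against 200 stated. That is a separate matter. It is relevant here only because 100 per arm would give 80% power at an SD of about 126 mg, so I show that SD as well.

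**Use lost by one patient discharged at 72 hours.**
- Flat use: 250/96 = 2.604 mg/h; × 24 h = 62.5 mg, so *f* = 0.25.
- Last-day use half the average: 31.25 mg, so *f* = 0.125.

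**Arm level.** Apparent mean = true mean × (1 − *p* × *f*). With no true effect, the false difference is 250 × *f* × (difference in *p*). With 100 per arm and SD 50, SE = 50 × √(2/100) = 7.07 mg. The two-sided false-positive rate is Φ(d/SE − 1.96) + Φ(−d/SE − 1.96), holding the SD fixed.

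| Arm difference in early discharge (assumed) | *f* | False difference in means | False-positive rate, SD 50 |
|---|---|---|---|
| 10 points | 0.125 | 3.1 mg | 7% |
| 10 points | 0.25 | 6.25 mg | 14% |
| 20 points | 0.125 | 6.25 mg | 14% |
| 20 points | 0.25 | 12.5 mg | 42% |

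At SD 126 (SE 17.8 mg) the rate is about 5% for 3.1 mg and 11% for 12.5 mg.

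**Equal early discharge.** With 30% in each arm and *f* = 0.25, the means become 250 × 0.925 = 231.25 and 200 × 0.925 = 185. The true 50 mg difference shrinks to 46.25 mg, and under the null there is no false difference.

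**Check on a per-hour alternative.** In the half-rate case a patient discharged at 72 hours has used 250 − 31.25 = 218.75 mg, or 218.75/72 = 3.04 mg/h, against 2.60 mg/h over the full 96 hours. The rate is about 17% too high, so dividing by observed hours is not a complete cure.

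**The case against.** The strongest reply is that the window can be inferred. The sizing paragraph sits in section 11 and identifies the 96-hour requirement with the primary outcome, and section 6 schedules pain assessments and coordinator follow-up over the same 96 hours. This stands as far as it goes: a reader might infer that section 11 contains no window at all, and that would be wrong. But inferring 96 hours supplies neither time zero nor a rule for hours that are not observed.

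It is also fair to say that the plan never prescribes a sum cut off at discharge, that opioid use while in hospital is a legitimate quantity if declared, and that these are multi-system trauma patients with poor inspiratory capacity for whom 72 hours is a minimum anticipated stay. How often truncation would occur is unknown. These points limit the size of the problem. They do not remove it, because data collection stops at discharge and the only written rule for incomplete data is truncation at withdrawal.

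Three stronger readings are tempting and not supported:
- That the 62.5 mg lost at 72 hours outweighs the 50 mg design effect. The first is one patient's shortfall under flat use; the second is a difference between arm means. The arm-level figures are the ones to compare.
- That bias is certain. It needs early discharge to differ by arm.
- That the inclusion criterion must rise to 96 hours. An anticipated stay does not prevent actual early discharge, and the criterion's clock need not start at injection.

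The telemetry wording is a separate inconsistency. Section 6 lets monitoring end at discharge, while section 9 has it run "for the first 96 hours at minimum". Those passages must be reconciled, but they are not evidence about the endpoint.

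**Conclusion.** The concern holds as a gap in the endpoint definition and in the handling of incomplete data. The endpoint sentence lacks a window and time zero, and a cumulative 96-hour total from the data as collected would count hours after discharge or withdrawal as zero use.

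The likely direction, if the drug shortens stay as hoped, is in the drug's favour. For arm differences of 10 to 20 points in discharge at 72 hours, the false difference is 3.1 to 12.5 mg, or 6% to 25% of the 50 mg target. The false-positive rate is about 7% to 42% at the stated SD, and lower if the true SD is larger. With equal early discharge the cost is modest dilution. All these sizes rest on assumed discharge shares and an assumed time course of opioid use. A reader might infer that the trial's result will be biased by a known amount; the documents do not support that, because they give no early-discharge share.

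**What to change.** In section 11, define the primary endpoint as total oral morphine equivalents from the end of injection (time zero) to 96 hours. Then:

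1. Pre-specify that hours after discharge, withdrawal or death are not counted as zero use, and name the method the primary analysis uses for them.
2. Continue recording opioid use to 96 hours for withdrawn patients who are still in hospital and agree to it.
3. Report the number discharged before 96 hours by arm.
4. Add pre-specified sensitivity analyses: (a) use over a common early window observed in nearly all patients, for example 0–48 or 0–72 hours; (b) use per observed hour, noting that it overstates use for early-discharged patients if use declines; (c) the discharge opioid prescription as an upper bound for the remaining hours, since a prescription is not consumption.

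Leave the eligibility criterion as it is, and reconcile the telemetry wording in sections 6 and 9 separately. The cost is protocol wording, a little more data entry and a few extra analyses; the sample size and eligible pool do not change.

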emergency medicine and surgery practitioners are familiar with intercostal blocks for placement of tube thoracostomy. Intercostal blocks do not require additional training, as would be done in the setting of a pain medicine fellowship, and do not incur the risks of hypotension associated with epidural catheters. Additionally, intercostal and paravertebral blocks carry similar risks of pneumothorax or intercostal neurovascular bundle injury.

Study design:

This is an investigator-initiated, single-center, prospective, double-blinded, placebo-controlled trial funded by the United States Air Force. Multi-system, adult trauma patients greater than or equal to 18 years of age admitted to the University of Cincinnati Medical Center (UCMC), an urban American College of Surgeons-verified Level 1 trauma center with more than 3500 annual trauma admissions annually will be identified by the research team. Patients will be screened and those who meet all inclusion/exclusion criteria will be approached for informed consent by study personnel in their rooms. Informed consent will be obtained prior to enrollment and any study procedures are done. Patients will then receive either receive 1 mL of liposomal bupivacaine just below each affected rib or 0.9% sodium chloride peri-intercostal subcutaneous injection (as placebo control) via a 25-G needle. Goal enrollment is 200 patients with 100 patients in each group. Patients included in the study will be followed during inpatient hospitalization through discharge.

6. Research data collection/study procedures:

Intervention

Patients will be identified on admission and will be screened by inclusion/exclusion criteria. After informed consent is obtained they will be randomized into one of two possible groups:

- a. Liposomal bupivacaine intercostal (group 1; interventional)
- b. 0.9% sodium chloride peri-intercostal subcutaneous (group 2; placebo-control)

Patients will be placed on continuous monitoring of heart rate, EKG, and pulse oximetry. Blood pressure and respiratory rate will be measured every 5 to 10 minutes during the procedure and every at least 15 minutes for the first hour after the procedure. All patients undergoing injection will remain on heart rate, EKG, and pulse oximetry monitoring by telemetry for 96 hours following injection.

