In addition, while in the ICU all study subjects will be monitored with a non-invasive respiratory monitor (Expiron) to determine respiratory rate, tidal volume, minute volume and breathing pattern for up to 96 hours. This monitoring will aid in

detection of respiratory depression and add additional safety to the trial. This device measures chest expansion by thoracic impedance and is FDA approved.

Supplemental oxygen will be provided to maintain a peripheral oxygen saturation of 90% or greater.

Injections will be performed by trained trauma / critical care physicians. Training prior to initiating the study will include familiarization with the standardized procedure as described below, which will be documented in study records. Patients will be monitored by bedside nurses before, during, and after the block procedure. Standard inpatient cardiac arrest carts will be immediately available before, during, and after the block procedure.

A 20-mL vial will be obtained from IDS Pharmacy that either contains liposomal bupivacaine (266 mg in 20-mL) or 0.9% sodium chloride. Patients will be positioned either sitting up or in logroll/decubitus position. Rib fractures will be noted from previously obtained CT scan of the chest from initial trauma evaluation. The thoracic posterolateral area will be prepped and draped in sterile fashion. After aspiration to prevent intravascular injection, 1 mL of liposomal bupivacaine will be injected with a 25-G needle just below each affected rib by the intercostal neurovascular bundle in a posterior but not paravertebral position or 0.9% saline (as placebo control) will be injected with a 25-G needle in the subcutaneous space just superficial to each affected rib to minimize risk of placebo-injection complications. Optimal regional blockade will include the rib immediately above the most superior and the rib immediately below the most inferior fractured rib.

Regional blockade will only be performed once per patient enrolled in the study and at one injection site per fractured rib. Patients will only be enrolled once per acute traumatic event and admission.

If a patient enrolled in the study should have an adverse event during the course of intercostal rib block administration and the reaction is severe or life-threatening, then the patient will be withdrawn from the study and no further injections will be administered, regardless of how many injections were originally planned.

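### Opioid use after withdrawal is left out of an intention-to-treat analysis whose primary outcome is sized as a 96-hour total, and the handling of partial totals is not stated

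*Combined protocol and SAP*

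**What the plan says.** Section 11 (Data Analysis) states: "An intention-to-treat model will be used for data analysis". Shortly afterwards it adds: "Patients withdrawn from the study will have data included up to the point of withdrawal".

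The primary endpoint in the same section is: "Compare opioid requirements (in morphine equivalents) between trauma patients with rib and/or sternal fractures receiving liposomal bupivacaine versus standard of care". It has no time window. The only window attached to the outcome is in the sample-size paragraph: "Assuming a 96-hour requirement of 250-mg oral morphine equivalents". The analysis is a t-test or, in the plan's words, "rank sum/Kruskal-Wallis ANOVA for normally distributed and non-normally distributed data, respectively as appropriate". No section says how a partial total enters that test. There is no scaling per hour, no imputation and no sensitivity analysis.

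Patients can leave by several routes:

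- After a severe or life-threatening reaction during the block, "then the patient will be withdrawn from the study and no further injections will be administered" (Section 6, Intervention; repeated in Section 9, Level of Risk).
- Section 9 discontinues a subject at once for a non-sinus rhythm or ST change. It does not say whether data collection stops too.
- Section 14 adds withdrawal at the patient's wish or at the trauma team's discretion, after which the patient receives standard of care. The analgesic ladder in Section 6 shows that this includes opioids.

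Section 6 also provides daily follow-up for 96 hours after the block, telemetry for the same period ("pulse oximetry monitoring by telemetry for 96 hours following injection"), and follow-up of serious adverse events until they resolve.

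**The concern.** For a cumulative dose, cutting the record short lowers the value, and a lower value is the favourable result. A patient withdrawn during the injections would carry a recorded total near zero while still receiving opioids on the ward. Compared as a complete 96-hour total, that patient counts among the best outcomes in the arm.

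The intention-to-treat question is how much opioid patients need over 96 hours according to the arm they were assigned to, whatever happened to their study procedures. The rule as written does not answer it, although the missing part is routine medication-record data on patients who are mostly still in hospital.

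The same gap arises when discharge or death cuts the window short. Early discharge is foreseeable: Section 13 requires an anticipated stay of only 72 hours, and follow-up ends at discharge.

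**Working it through.** **Inputs from the documents (Sections 5 and 11).** 100 patients per arm; 96-hour means of 250 mg (control) and 200 mg (active); SD 50 mg; alpha 0.05; power 80%. No withdrawal rate is given, so every count below is an assumption, written active v placebo. The tests are taken as two-sided, which the plan does not state.

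**The plan's own sample size.** n per arm = 2 × (1.960 + 0.842)² × (50/50)² = 15.7, so 16 per arm and 32 in total. The stated 200 is not reproduced. That is a separate matter and is used here only to obtain a second SD. With 100 per arm and 80% power, a 50 mg difference fits an SD of 50 / [√(2/100) × 2.802] = 50 / 0.396 = 126 mg. I use 50 mg (the plan's value) and 126 mg (an assumption).

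**Which counts to try.** Section 10 stops the study if "Serious/life-threatening adverse events, regardless of causality, occur in > 2% of enrolled patients". In 200 patients, 4 is exactly 2% and does not cross that line, so 4 is the most serious events the rule allows. It does not cap rhythm, voluntary or discretionary withdrawals that are not serious events. A 4 v 4 split (8 patients) would have to include some of those.

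**Expected means if partial totals are compared as they stand.** Observed arm mean = true mean × [1 − w(1 − f)], where w is the share withdrawn and f the share of the 96-hour total recorded. At hour 0, f = 0.

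No drug effect (250 mg in both arms):
- 4 v 0: 250 − 250 × 0.96 = 10 mg in favour of the drug; 0 v 4 is the mirror image.
- 3 v 1: 247.5 − 242.5 = 5 mg. 2 v 0: 250 − 245 = 5 mg.
- 4 v 0 spread evenly over 96 hours (average f = 0.5): 5 mg.
- 4 v 4: 0 mg.

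True effect of 50 mg (200 v 250):
- 4 v 0: 250 − 192 = 58 mg (inflated).
- 4 v 4: 240 − 192 = 48 mg (diluted).
- 5 v 4: 240 − 190 = 50 mg (unbiased, although the counts differ).
- 0 v 4: 240 − 200 = 40 mg (shrunk).

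**Error rates by simulation.** Withdrawal counts were fixed and outcomes were normal, floored at zero. The t-test was used if a Shapiro-Wilk test passed in both arms, otherwise the rank-sum test. This is an assumed reading of Section 11, which names no normality check.

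| No drug effect | Type I error, SD 50 | SD 126 |
|---|---|---|
| none | 5.0% | 5.2% |
| 4 v 0, hour 0 | 6.9% | 7.4% |
| 0 v 4, hour 0 | 7.6% | 8.4% |
| 4 v 0, spread | 6.8% | 5.9% |
| 2 v 0, hour 0 | 5.6% | 5.6% |
| 3 v 1, hour 0 | 5.0% | 5.1% |
| 4 v 4, hour 0 | 3.5% | 3.6% |

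| True 50 mg effect, SD 126 | Power |
|---|---|
| none | 78.7% |
| 4 v 4, hour 0 | 73.3% |
| 0 v 4, spread | 68.8% |
| 1 v 3, hour 0 | 67.7% |
| 0 v 4, hour 0 | 57.6% |

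At SD 50, power stays above 99% even with 0 v 4. A separate, smaller re-run agreed within simulation error.

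**The case against.** The strongest reply is that the sentence keeps withdrawn patients in the analysis instead of dropping them. It says which data are used, not that a truncated sum is treated as a 96-hour total. This stands in part: the bias is conditional on comparing raw partial totals, which the plan neither states nor excludes. It does not rescue the rule, because the rule still ends the count at withdrawal when the rest of the record could be obtained. A single total per patient, compared by t-test or rank-sum, also has no built-in way to handle a short window.

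A second reply is that the effect is small. That is true at low withdrawal rates, and at the planned SD of 50 mg there is no power cost.

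Three stronger readings are tempting, and the documents do not support them.

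- *That the rule favours the drug.* The active injection is placed deeper than the placebo (Section 6), so more active-arm withdrawals are plausible. But the tables in Section 9 show no excess: serious events 1.1% v 1.1%, and any event 59.8% v 67.7% and 16.8% v 18.1%, drug v placebo. Voluntary or discretionary withdrawal could be commoner on placebo.
- *That the arm losing more patients always gains.* This is exact only with no drug effect. With the planned effect, 5 v 4 at hour 0 is unbiased and 4 v 4 is diluted.
- *That type I error is badly inflated.* With 10 v 0 withdrawn, a quarter of the total recorded and SD 50, a t-test alone gives about 55%. Under the plan's test choice, read as above, it is about 21%, and nothing in the documents supports a 10 v 0 split.

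**Conclusion.** The point holds and should be fixed before the analysis. The stated withdrawal rule does not deliver the promised intention-to-treat effect on an endpoint sized over 96 hours, and it leaves out opioid use that could be obtained.

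The inconsistency is certain; its size is not. It depends on unknown withdrawal counts and on raw partial totals being compared. At 4 v 0 or 0 v 4 at hour 0, the spurious difference is about 10 mg and type I error about 7-8%. At 3 v 1 or with equal losses there is essentially no inflation. Power loss matters only if the true SD is well above 50 mg: at an assumed 126 mg, about 79% falls to 73% with 4 v 4 and 58% with 0 v 4. The direction cannot be settled from the documents.

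**What to change.** 1. Define the primary endpoint as total oral morphine equivalents over 96 hours from the block procedure. For a patient randomised but not injected, start the clock at randomisation or at a stated planned injection time; otherwise that patient has no time zero.

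2. Replace the withdrawal sentence in Section 11 with: *Patients whose study procedures are stopped remain in follow-up for data collection; opioid use to 96 hours is taken from the medication record for every randomised patient in both arms who is still in hospital. Data stop at withdrawal only when the patient withdraws consent for data use.* Reconcile the withdrawal and discontinuation wording in Sections 6, 9 and 14 with this, without changing clinical management. Check that the consent form allows record use after study procedures stop.

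3. Do not analyse a total cut short by discharge, death or withdrawn data consent as a complete 96-hour total. Count such cases by arm, fix their primary handling before unblinding, and report one sensitivity analysis. The choice of method is left to the authors.

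The cost is some wording, a little record abstraction for the few withdrawn patients, the consent-form check and one extra analysis. Sample size does not change. Totals cut short by discharge, death or withdrawn data consent stay incomplete; the change makes them visible but does not recover them.
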